10.7.7 Electrocardiograms Analysis

The number and percentage (n, %) of subjects who have Investigator's interpretation of ECG 'Normal', 'Abnormal/Not Clinically Significant' and 'Abnormal/Clinically Significant' will be presented by treatment group and overall at baseline and visit 6/ET.

A listing of Investigator's interpretation of ECG results and a listing of ERT ECG results will be provided.

10.7.8 Safety Visit Question

The answers Yes/No to the question "Does the subject exhibit signs and symptoms of possible contact sensitization?" at Visit 3 and Visit 5 will be listed.

10.8 Other Assessments Analysis

10.8.1 Satisfaction Questionnaires Analysis

Number and percentage (n, %) of subjects for each answer of each question of the satisfaction questionnaires will be presented by treatment group and overall at visit 4 (4b if applicable, second DL-PDT) and visit 6/ET.

A listing of all satisfaction questionnaires data will be provided.

10.8.2 Weather Assessment

A listing of all weather assessment data will be provided.

Statistical Analysis Plan**10.8.3 Subject's Skin Aspect Analysis**

Scores of clinical assessment of subject's skin aspect collected at Visit 6/ET will be summarized by treatment group and overall by reporting the number and percentage of subjects (n, %) for each score. For the aim of summary, the worst score among all the assessed lesions of each subject will be taken into account.

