#### 9.2.4.2 Adverse Events of Special Interest (AESIs)

An AESI is a noteworthy event for the particular study drug that can be appropriate to monitor closely. It could be serious or non-serious and AESIs could include events that might be potential precursors or prodromal symptoms for more serious medical conditions in susceptible individuals.

The AESIs for this protocol have been predefined as follows:

- Contact sensitization see [Section 9.4.4](#)

At each visit, particularly Visits 3 and 5, the Investigator should examine the treatment area(s) carefully and be aware of the potential for contact irritation and contact sensitization. Contact sensitization is an AESI. For AESIs, the Investigator is required to complete the Adverse Event Form in the eCRF, within 72 hours of the event, otherwise follow the SAE reporting procedures in [Section 9.2.4.3](#), even if the event is considered non-serious according to the usual regulatory criteria.

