#### 10.1.3.5 Other Assessments Analysis

The subject questionnaires at Visit 4 (second DL-PDT) and Visit 6 (Final Visit) will only be descriptively summarized. The Clinical Assessment of the Subject's Skin Aspect evaluated by the investigator at Visit 6 will only be descriptively summarized. The subject exposure time and PpIX effective dose at Visit 2 and Visit 4 will only be descriptively summarized.

---

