6 EFFICACY AND SAFETY VARIABLES

6.1 Efficacy Variables

6.1.1 Lesion Response

At Visit 2 (before treatment), the Investigator will map the subject's lesions, count them, and report their severity according to criteria based on Olsen (1991) (see Table 2).

At Visits 2b (if applicable), 4, 4b (if applicable) before treatment and at Visit 6/ET, the severity of pre-existing, treated AK lesions that had been identified and treated previously will be recorded. If new AKs develop in the treatment area, they will be recorded, but not treated nor included into the efficacy evaluations.

Table 2 - Lesion Severity Grade Scale

Grade	Severity	Description
Grade 1	Mild	Slightly palpable, better felt than seen
Grade 2	Moderate	Moderately thick, easily felt and seen
Grade 3	Severe	Very thick and/or obvious actinic keratoses

The Investigator will be asked at Visits 2b (if applicable), 4, 4b (if applicable) and 5/ET to identify each lesion treated previously, and the lesion response as a CR or a non-CR, as described in Table 3.

Table 3 - Lesion Response Score

Response	Score	Description
Complete response (CR)	1	Complete disappearance of the lesion, visually and by palpation
Non-complete response (non-CR)	0	Non-complete disappearance of the lesion

If all of the treated lesions in the treatment area are assessed to be CR at 12 weeks after the last DL-PDT session (Visit 6), the subject will be assessed as a subject CR. If any of the treated lesions in the treatment area are assessed to be non-CR, the subject will be assessed as a non-complete responder. Those subjects who are assessed to be CR, i.e., all treated lesions cleared, at Visit 6 will be offered the opportunity to continue in the long-term follow-up study, to assess recurrence of lesions treated.

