6.2.3 Clinical assessment of the subject's skin aspect

At Visit 6, for each lesion that has responded completely (see Table 3), the Investigator will assess the subject's skin aspect on the following signs: scarring, atrophy, induration, redness or change in pigmentation (see Table 5).

The clinical assessment of skin aspect will be graded according to the following scale.

Table 5 - Scale for Clinical Assessment of Subject's Skin Aspect

Clinical Assessment	Score	Description
Excellent	3	No scarring, atrophy or induration, and no or slight occurrence of redness or change in pigmentation compared to adjacent skin
Good	2	No scarring, atrophy or induration, but moderate redness or change in pigmentation compared to adjacent skin
Fair	1	Slight to moderate occurrence of scarring, atrophy or induration
Poor	0	Extensive occurrence of scarring, atrophy or induration

In the event of the score of 2 or less for the clinical assessment of subject's skin aspect, it will be recorded as an AE in the eCRF.

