6.2.4 Adverse Events

Adverse events (AEs) will be recorded during each visit (Visits 1, 2, 3, 4, 5 and 6/ET) and at other visits caused by postponement of treatment or incomplete treatment.

All medical events, whether observed by the Investigator or reported by the subject, and whether or not thought to be treatment-related, will be considered AEs and recorded on the appropriate AE form.

Statistical Analysis Plan

An AE is defined as any untoward medical occurrence in a clinical study, in which a subject is administered a medicinal product that does not necessarily have a causal relationship with this treatment. An AE can therefore be any unfavorable and unintended sign (including an abnormal laboratory finding), symptom, or disease temporally associated with the use of a medicinal (investigational) product, whether or not it is related to the medicinal (investigational) product. This includes an exacerbation of pre-existing conditions or events, intercurrent illnesses, drug interaction, or the significant worsening of the indication under investigation, that is not recorded elsewhere in the eCRF under specific efficacy assessments.

Refer to the study protocol for further details about AEs definition and management.

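### SAP 10.8.3 compares arms on each subject's worst skin-aspect score among cleared lesions, so among scored subjects the arm that clears more tends to look worse at equal risk per cleared lesion

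*SAP*

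**What the plan says.** SAP 6.2.3 (and protocol 9.2.3) limits the scoring: "At Visit 6, for each lesion that has responded completely", the investigator grades the skin from 3 (Excellent) to 0 (Poor). A lesion that did not clear gets no score, so a subject with no cleared lesion has none.

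SAP 10.8.3 summarises the scores by arm and overall "by reporting the number and percentage of subjects (n, %) for each score", and reduces each subject to one value: "the worst score among all the assessed lesions of each subject will be taken into account". That section does not say whether the percentage is of all subjects in the arm or of those with a score. It plans no count of subjects without a cleared lesion and no lesion-level summary. Nor does it plan a listing, although 10.8.1, 10.8.2 and 10.8.4 each do.

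SAP 8.2 puts safety data on the safety population. Skin aspect is a safety variable in SAP 6.2 but is analysed under Other Assessments in SAP 10.8, and neither place says how an unscored subject counts. Protocol 10.1.3.5 sets the status of the analysis: skin aspect "evaluated by the investigator at Visit 6 will only be descriptively summarized".

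**The concern.** The minimum of k scores falls as k rises. Here k is the number of cleared lesions, which is what the treatment is meant to increase. The by-arm comparison therefore mixes two things: how often a cleared site looks poor, and how many sites were cleared and so could be scored. The second is efficacy, but in this table it reads as harm.

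The open denominator adds a second problem. More vehicle than MAL subjects are likely to have no cleared lesion. On an all-subjects base they drop out of every score category, Excellent included.

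Safety is part of the primary objective (SAP 3.1), and this is the only dedicated by-arm summary of scarring, atrophy, induration, redness and pigment change at cleared sites. At stake is how that table is read. No test or claim rests on it.

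**Working it through.** **The plan's own figures.** The documents give no figure for skin aspect. The response rates used here come from SAP 9, whose sample-size figures reproduce. MAL subjects completing long-term follow-up: 380 × 0.93 × 0.45 × 0.70 × 0.90 = 100.2, against approximately 100 stated. Power for 45% vs 15% with 380:190 at two-sided 0.00125 exceeds 0.9999, against more than 90% stated.

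**Inputs from the documents.** Subject complete response 45% MAL and 15% vehicle (SAP 9); 4 to 12 treated lesions, 8 taken as the base case; MAL lesion clearance 70.1% (protocol 6.2.1, European study, after one treatment).

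**Assumptions not in the documents.** Vehicle lesion clearance 30, 40, 50 or 60%; the same risk q = 2% of a score of 2 or less per cleared lesion in both arms; scores independent within a subject, relaxed below.

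**Method.** Cleared lesions K out of n = 8 follow a beta-binomial with the stated mean, its spread solved so that P(K = 8) is 0.45 (MAL) or 0.15 (vehicle). Then

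- all subjects: P(worst score ≤ 2) = 1 − Σ P(K = k)(1 − q)^k
- scored subjects: the same, divided by 1 − P(K = 0)
- Excellent, all subjects: Σ P(K = k)(1 − q)^k − P(K = 0)

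| | MAL (70.1%) | Veh 30% | Veh 40% | Veh 50% | Veh 60% |
|---|---|---|---|---|---|
| P(no cleared lesion) | 0.099 | 0.526 | 0.319 | 0.150 | 0.043 |
| Expected scored subjects | 342 of 380 | 90 of 190 | 129 | 161 | 182 |
| Score ≤ 2, % of scored | 11.7 | 9.6 | 8.9 | 9.0 | 9.6 |
| Ratio MAL/vehicle, scored | – | 1.22 | 1.31 | 1.31 | 1.23 |
| Score ≤ 2, % of all | 10.6 | 4.5 | 6.1 | 7.6 | 9.1 |
| Excellent, % of all | 79.6 | 42.8 | 62.1 | 77.4 | 86.5 |
| Score ≤ 2, % of cleared lesions | 2.0 | 2.0 | 2.0 | 2.0 | 2.0 |

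Scored counts take every randomized subject as assessed at Visit 6. The mechanism shows in the mean number of cleared lesions per scored subject: 8 × 0.701/0.901 = 6.2 for MAL, against 8 × 0.30/0.474 = 5.1, 8 × 0.40/0.681 = 4.7, 8 × 0.50/0.850 = 4.7 and 8 × 0.60/0.957 = 5.0 for vehicle.

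**How far the scored-subject ratio moves.**

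- 4, 8 or 12 lesions and q of 1, 2 or 5%, with the clearance values above: 1.19 to 1.32.
- Lesions clearing independently at rates implied by 45% and 15% (0.45^(1/8) = 0.905; 0.15^(1/8) = 0.789): 1 − (1 − 0.905 × 0.02)^8 = 13.6% vs 1 − (1 − 0.789 × 0.02)^8 = 11.9%, ratio 1.14. At q = 10% it is 1.10. With 12 lesions and q = 20% it falls to 1.03 (91.7% vs 89.4%).
- MAL clearance 89.2% (protocol 6.2.1, Australian study, mild lesions), 8 lesions, q = 2%: 1.40 to 1.50.
- Correlated scores within a subject (beta-binomial on q, base case): 1.13 to 1.20 at a correlation of 0.3, 1.09 to 1.15 at 0.5, and 1.0 when all cleared lesions of a subject share one score.

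**The case against.** **The artefact is modest.** The base-case gaps among scored subjects are 2.1 to 2.8 percentage points, against a standard error of about 2.8 to 3.6 points with 342 scored MAL and 90 to 182 scored vehicle subjects. Lesions on one face share skin, sessions and usually a rater, so correlated scores are plausible. Protocol 6.3 also says most phototoxic signs with conventional PDT lasted 1 to 2 weeks, and scoring is at 12 weeks. This stands, and it keeps the point minor.

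**Among scored subjects the bias runs against the sponsor's product, and nothing depends on the table.** Also true. It is still a distorted comparison that data already collected can put right.

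**The denominator may be set elsewhere.** SAP 12 and 13.1 place analysis details in shells kept as a separate document. So one can say only that SAP 10.8.3 states none. Stating it would not remove the dependence on the number of cleared lesions.

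**Stronger readings that a reader might infer.**

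- That MAL looks worse throughout the table. Not on an all-subjects base: MAL then shows more Excellent subjects in three of the four scenarios (79.6% against 42.8, 62.1 and 77.4%; the fourth is 86.5%).
- That the inflation is a settled 20 to 30%. Vehicle clearance, the risk and the correlation are all assumed, and the 70.1% follows one treatment where this trial gives two.
- That the TEAE comparison is inflated as well, because for a score of 2 or less in "skin aspect, it will be recorded as an AE in the eCRF" the rule feeds the AE tables. The documents do not support a direction. SAP 6.2.4 collects AEs regardless of clearance ("All medical events, whether observed by the Investigator or reported by the subject"), and at each visit "the Investigator should examine the treatment area(s) carefully and be aware of the potential for contact irritation and contact sensitization" (protocol 9.2.4.2). At 2% risk the excess is 6.0 to 1.4 points if nothing is captured at non-cleared sites and 0 at full capture. Allow for subjects already counted for other local AEs, taking 45% of MAL (protocol 6.2.1) and an assumed 10 to 20% of vehicle, independent of skin aspect. With no capture at non-cleared sites, the any-TEAE difference then moves by between +2.2 and −2.4 points.

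**Conclusion.** The point holds for subjects with at least one cleared lesion. At equal risk per cleared lesion, the worst-score rule tends to give the arm that clears more a higher percentage with a score of 2 or less. The ratio is roughly 1.03 to 1.5 with independent scores and tends to 1.0 as within-subject correlation approaches 1. The direction needs only that MAL's scored subjects have more cleared lesions each and that scores are not perfectly correlated; the size rests on assumptions the documents do not supply. On an all-subjects base the table has no single direction of distortion. The summary is descriptive, and the primary and gated secondary endpoints are untouched. Severity is minor: a cheap improvement to how a safety-relevant table reads.

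**What to change.** Amend SAP 10.8.3 and the matching shell, before unblinding, to:

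1. add the distribution of scores 3, 2, 1 and 0 by arm with cleared lesions as the denominator;
2. report by arm the number of subjects with no cleared lesion;
3. keep the worst-score table, with subjects having at least one cleared lesion as its stated denominator.

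The lesion scores are already collected under SAP 6.2.3. The cost is a few lines of SAP text and one more descriptive table. That table remains conditional on response, since only cleared lesions enter it, and should say so in a footnote. No supplementary TEAE tables and no table of all treated lesions are needed. The protocol asks only for a descriptive summary, so under SAP 11 an SAP update should suffice without a protocol amendment.

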10.8.4 Subject Exposure Time and PpIX Effective Dose Analysis

Descriptive statistics (n, mean, standard deviation, median, first and third quartile, min and max) by treatment group and overall will be presented for subject exposure time and PpIX effective dose at visit 2 (2b, if applicable) and visit 4 (4b, if applicable).

A listing of all subject exposure times and PpIX effective doses will be provided.

10.8.5 Suspected Sensitization (Rechallenge and Patch Ingredient Test)

Rechallenge patch test and ingredient patch test information will be presented in separate listing.

11 CHANGES FROM THE PROTOCOL ANALYSIS PLAN

Any change from the protocol will be justified and fully documented.

If the blind review suggests changes to the principal features stated in the protocol, these have to be documented in a protocol amendment. Otherwise, it will suffice to update the statistical analysis plan with the considerations suggested from the blind review.

Statistical Analysis Plan**12 SHELLS OF TABLES, FIGURES AND LISTINGS AND REPORTING OUTPUT (GENERAL FEATURES)**

Tables, figures and listings will be generated using SAS® and will be displayed on A4 size paper with landscape orientation, 2 cm for top and bottom margins, 0.8 cm for left and right margins and 8pt Courier New font.

The header section will comprise the sponsor's name, the protocol number, the delivery description, the TFL number, the TFL title, the population and the page number (Page X of Y). The footer section will include the TFL footnotes, the data extract date (if applicable), the date and time of the execution of the program, and the name of the program.

A clear, accurate and complete programming code will be developed to generate the statistical analyses, summary tables, figures and listings to be integrated in the report. Fluent use of precise titles and footnotes will be made to improve the understanding of summaries and document any assumption. Details of analysis specifications including but not limited to the SAS code will be documented on the shells.

Statistical Analysis Plan

13 APPENDICES

13.1 Shells for Table, Figure and Listings

The final list of tables, figures and listings and their shells for the reporting of this study will be available in a separate document that will be developed and will be finalized before database lock.

13.2 Potentially Clinically Significant Values of Vital Signs

Criteria for identifying vital signs values as Potentially Clinically Significant Values are the following.

Table 10 - Potentially Clinically Significant Values of Vital Signs

Parameter	Criteria		Change Relative to Baseline
Pulse Rate	≥ 120 beats/min	and an	increase ≥ 20 beats/min
	≤ 50 beats/min	and a	decrease ≥ 20 beats/min
Systolic Blood Pressure	≥ 160 mmHg	and an	increase ≥ 20 mmHg
	≤ 95 mmHg	and a	decrease ≥ 20 mmHg
Diastolic Blood Pressure	≥ 110 mmHg	and an	increase ≥ 10 mmHg
	≤ 45 mmHg	and a	decrease ≥ 10 mmHg
Body Temperature	$\geq 38.3^\circ\text{C}$	and an	increase $\geq 1.1^\circ\text{C}$
	$\geq 101^\circ\text{F}$	and an	increase $\geq 2^\circ\text{F}$

13.3 Potentially Clinically Significant Values of Laboratory Tests

Criteria for identifying laboratory test values as Potentially Clinically Significant Values are the following.

Table 11 - Potentially Clinically Significant Values of Laboratory Tests

Parameter	Sex	Criterion Values	
		Standard Units	SI Units
Blood Chemistry			
Aspartate Aminotransferase	Male and Female	$> 3 \times \text{ULN}$	$> 3 \times \text{ULN}$
Alanine Aminotransferase	Male and Female	$> 3 \times \text{ULN}$	$> 3 \times \text{ULN}$
Alkaline Phosphatase	Male and Female	$> 400 \text{ U/L}$	$> 400 \text{ U/L}$
Gamma Glutamyltransferase	Male and Female	$> 3 \times \text{ULN}$	$> 3 \times \text{ULN}$
Lactate Dehydrogenase	Male and Female	$> 3 \times \text{ULN}$	$> 3 \times \text{ULN}$
Urea	Male and Female	$> 64 \text{ mg/dL}$	$> 10.7 \text{ mmol/L}$
Blood Urea Nitrogen	Male and Female	$> 29.9 \text{ mg/dL}$	$> 10.7 \text{ mmol/L}$
Creatinine	Male and Female	$> 2.0 \text{ mg/dL}$	$> 176.8 \text{ }\mu\text{mol/L}$

Statistical Analysis Plan

Parameter	Sex	Criterion Values	
		Standard Units	SI Units
Creatinine Kinase	Male and Female	> 2.5 x ULN	> 2.5 x ULN
Uric Acid	Male	> 10.0 mg/dL	> 0.5948 mmol/L
	Female	> 8.0 mg/dL	> 0.4758 mmol/L
Total Bilirubin	Male and Female	> 2.0 mg/dL	> 34.2 μ mol/L
Albumin	Male and Female	< 25 g/L	< 3.63 μ mol/L
Sodium	Male and Female	< 130 mmol/L	< 130 mmol/L
		> 150 mmol/L	> 150 mmol/L
Potassium	Male and Female	< 3.0 mmol/L	< 3.0 mmol/L
		> 5.5 mmol/L	> 5.5 mmol/L
Calcium	Male and Female	< 7 mg/dL	< 1.75 mmol/L
		> 12 mg/dL	> 3.00 mmol/L
Chloride	Male and Female	< 90 mmol/L	< 90 mmol/L
		> 118 mmol/L	> 118 mmol/L
Glucose	Male and Female	< 50 mg/dL	< 2.78 mmol/L
		> 250 mg/dL	> 13.88 mmol/L
Total Cholesterol	Male and Female	> 300 mg/dL	> 7.77 mmol/L
Low-Density Lipoprotein	Male and Female	> 160 mg/dL	> 4.14 mmol/L
High-Density Lipoprotein	Male and Female	< 30 mg/dL	< 0.78 mmol/L
Triglycerides	Male and Female	> 300 mg/dL	> 3.39 mmol/L
Hematology			
Hematocrit	Male	\leq 37%	\leq 0.37 L/L
	Female	\leq 32%	\leq 0.32 L/L
Hemoglobin	Male	\leq 11.5 g/dL	\leq 115 g/L
	Female	\leq 9.5 g/dL	\leq 95 g/L
Platelets	Male and Female	\leq 75 $10^3/\mu$ L	\leq 75 $10^9/L$
		\geq 700 $10^3/\mu$ L	\geq 700 $10^9/L$
Leukocytes	Male and Female	\leq 2.8 $10^3/\mu$ L	\leq 2.8 $10^9/L$
		\geq 16 $10^3/\mu$ L	\geq 16 $10^9/L$
Eosinophils	Male and Female	> 1.0 $10^3/\mu$ L	> 1.0 $10^9/L$
Neutrophils	Male and Female	< 1.5 $10^3/\mu$ L	< 1.5 $10^9/L$

